## **7.5        SECONDARY ENDPOINT(S)**

### **7.5.1      Key secondary endpoint(s)**

This section is not applicable as no key secondary endpoint has been specified in the protocol.

### **7.5.2      (Other) Secondary endpoint(s)**

#### **7.5.2.1    Phase Ia**

*PK parameters evaluated after the first and after multiple administrations of BI 754091*

The PK parameters will be evaluated using noncompartmental analysis methods according to 001-MCS-30-476 (2). Tables and figures for concentration values and PK parameters will be created according to 001-MCS-30-476 (2).

Descriptive statistics will be calculated for all concentration time points and PK parameters. The following descriptive statistics will be calculated for BI 754091 concentrations: N (number of patients with non-missing values), arithmetic mean, standard deviation, minimum, median, maximum, arithmetic coefficient of variation, geometric mean, and geometric coefficient of variation and for PK parameters: N, arithmetic mean, standard deviation, minimum, median, maximum, tenth percentile (P10), Q1, Q3, ninetieth percentile (P90), arithmetic coefficient of variation, geometric mean, and geometric coefficient of variation.

The PKS will be used for PK analysis. Non evaluable patients will be listed with their individual PK parameters, but such data will not be included when calculating descriptive statistics.

*Objective response according to RECIST v1.1*

Objective response will be analysed in terms of ORR, defined as the proportion of patients with best overall response of CR or PR.

ORR according to RECIST v1.1 will be summarised descriptively with 95% exact Clopper-Pearson CIs.

*Number of patients experiencing DLTs from the start of treatment until end of treatment*

Number of patients with DLT(s) which occurred during the entire treatment period will be summarised for each dose cohort.

**7.5.2.2 Phase Ib**

*Progression-free survival by RECIST 1.1*

PFS will be summarized descriptively by quartiles with 95% confidence interval (based on the Greenwood's method) calculated from Kaplan-Meier estimate.

*Safety*

Number of patients with AEs, SAEs and clinical relevant abnormalities in vital signs, laboratory evaluations or ECG parameters as reported by the investigator as AEs will be summaries for each cohort.

Please refer to [Section 7.5.2.1](#).

## **7.7 EXTENT OF EXPOSURE**

The total number of administrations, total number of cycles initiated and treatment duration of BI 754091 will be summarized descriptively for each dose cohort. Results of Ia and Ib will also be presented separately.

## **7.8 SAFETY ANALYSIS**

All safety analyses will be performed on the treated set (TS). Treated patients will be analysed according to their initial treatment.

Safety data recorded during the Residual Effect Period (REP) of 30 days will be considered as on-treatment.

Patients who were replaced within the MTD evaluation period will be excluded from the determination of the MTD but will be considered for all other safety evaluations.

### **7.8.1 Adverse Events**

The analyses of AEs will be descriptive in nature. All analyses will be based on the number of patients with AEs (not on the number of AEs). The analysis will be based on BI standards. AEs will be coded using the most recent version of MedDRA. The severity of AEs was assessed according to CTCAE Version 4.03 up to Amendment 4 and according to CTCAE Version 5.0 thereafter. AEs will be analysed as reported by the investigator and pooled independent of CTCAE version used if applicable.

The analyses of AEs will be based on the concept of treatment-emergent AEs, where a treatment-emergent AE has an onset in the analysing treatment period. The AE analysis will be based on the on-treatment period which starts with the date of the first administration of study medication and ends 30 days after the last administration of study medication. AEs with an onset date in the screening period (time between informed consent date and date of the first administration of study medication) or follow-up period (time after the on-treatment period) will be listed separately.

The actual planned dose of BI 754091 will be derived and included in the listings. AEs will be reported with start day and end day as calculated from the first day of treatment with study medication. For listings displaying AEs during the screening or follow-up period, the start and stop day are calculated from the start of the respective analysis period.

An overall summary of AEs will be presented.

Adverse events will be displayed by the initial dose of study medication administered on the first day of treatment.

The frequency of patients with adverse events during on-treatment period will be summarised by treatment, primary system organ class (SOC) and preferred term (PT) and by PT only (if at least 2 patients observed a repsecitive AE) for each of the following AE tables:

- DLTs
- All AEs by highest CTCAE grade
- Serious AEs by highest CTCAE grade
- Investigator assessed related AEs by highest CTCAE grade
- Investigator assessed related SAEs by highest CTCAE grade
- Investigator assessed AESI by highest CTCAE grade
- Investigator assessed immune-related AEs by highest CTCAE grade
- AEs leading to treatment discontinuation by highest CTCAE grade
- AEs leading to death

The SOC will be sorted alphabetically, preferred terms will be sorted by frequency (within SOC). Adverse events that are immune mediated can potentially begin more than 30 days after treatment. Additional tables will summarize all immune related events, including events with onset more than 30 days after the last treatment.

AEs leading to death during the on-treatment period will be tabulated by SOC and PT. Reported fatal AEs during follow-up period will be listed.

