5.3.6.8 Adverse event collection and reporting

5.3.6.8.1 Adverse event collection

The Investigator shall maintain and keep detailed records of all AEs in their patient files.

A schema of the safety follow-up period is presented in [Figure 5.3.6.8.1: 1](#). The following must be collected and documented on the appropriate eCRF by the Investigator:

- From signing the ICF onwards until the end of treatment (including the Residual Effect Period [REP]; a period of 30 days after the last dose of trial medication):
-all AEs (non-serious and serious) and all AESIs.
- After the EOT (including the REP) until the individual patient's end of trial:
-all related SAEs and all related AESIs.
- After the individual patient's end of the trial, the Investigator does not need to actively monitor the patient for AEs, but should only report relevant SAEs and relevant AESIs of which the Investigator may become aware of.

The rules for Adverse Event Reporting exemptions still apply.

[figure not shown]

Figure 5.3.6.8.1: 1 Safety follow-up schema

All AEs which occurred through the treatment phase and throughout the REP will be considered as on treatment; please see [Section 7.3.4](#). Events which occurred after the REP will be considered as post-treatment events.

Adverse event reporting to the sponsor and timelines

The Investigator must report SAEs, AESIs, and non-serious AEs that are relevant for the reported SAE or AESI, on the BI SAE form via secure e-mail connection or via fax immediately (within 24 hours) to the [REDACTED]

- Secure email [REDACTED] SAE mailbox: [REDACTED] or
- Fax [REDACTED] safety fax number: [REDACTED]

For sites outside of the US, country-specific fax numbers will be provided in the ISF/Study reference manual.

The same timeline applies if follow-up information becomes available. On specific occasions, the Investigator could inform the [REDACTED] upfront via telephone by calling the [REDACTED] SAE reporting phone number ([REDACTED]). This does not replace the requirement to complete and fax the BI SAE form.

With receipt of any further information to these events, a follow-up SAE form has to be provided. For follow-up information the same rules and timeline apply as for initial information.

Information required

For each AE, the Investigator should provide the information requested on the appropriate eCRF pages and on the BI SAE Report form. The Investigator should determine the causal relationship to the trial medication.

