7.3.4 Safety analyses

Adverse events will be coded using the Medical Dictionary for Regulatory Activities (MedDRA) coding dictionary. Standard BI summary tables and listings will be produced. Statistical analysis and reporting of AEs will concentrate on treatment-emergent AEs. All AEs with an onset between start of treatment and end of the REP, a period of 30 days after the last dose of trial medication, will be considered 'treatment-emergent' and assigned to the treatment period for evaluation. Adverse events that start before first drug intake and deteriorate under treatment will also be considered as 'treatment-emergent'.

All treated patients will be included in the safety analysis. In general, safety analyses will be descriptive in nature and will be based on BI standards. No hypothesis testing is planned.

Frequency, severity, and causal relationship of AEs will be tabulated by system organ class and preferred term after coding according to the current version of MedDRA.

Laboratory data will be analysed quantitatively as well as qualitatively. The latter will be done via comparison of laboratory data to their reference ranges. Values outside the reference range as well as values defined as clinically relevant will be highlighted in the listings.

Treatment groups will be compared descriptively with regard to distribution parameters as well as frequency and percentage of patients with abnormal values or clinically relevant abnormal values.

Vital signs, physical examinations, or other safety-relevant data observed at screening, baseline, during the course of the trial and at the end-of-trial evaluation will be assessed with regard to possible changes compared to findings before start of treatment.

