#### **4. CHANGES IN THE PLANNED ANALYSIS OF THE STUDY**

The CTP defines the primary endpoint in Phase Ia as number of patients experiencing DLTs graded according to Common Terminology Criteria for Adverse Events (CTCAE) Version 4.03 / 5.0 observed in the first cycle (3 weeks) in order to meet the objective of assessment of the maximum tolerated dose (MTD) of BI 754091. All patients in Phase Ia were assessed by CTCAE Version 4.03 and therefore CTCAE Version 5.0 is not applicable for the primary endpoint in Phase Ia.

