## **6. GENERAL ANALYSIS DEFINITIONS**

### **6.1 TREATMENT(S)**

In this Phase I trial, treatments are not randomized. Different dose levels of BI 754091 will arise in phase Ia and there is only one dose level in the 4 cohorts of phase Ib. Data of phase Ia and phase Ib will be displayed separately. In addition, for both phase Ia and phase Ib, data will be presented for all cohorts separately.

For phase Ia, the initial trial medication (i.e. dose level) assigned at the beginning of the first treatment cycle will be used as label of the analysing treatment.

Table 6.1: 1 Definition of analysing treatment periods for safety analysis

Analysing Treatment Period	Start Date	Stop Date
Screening	Date of informed consent	Date/Time of the first administration of trial treatment
On-treatment	Date/Time of the first administration of trial treatment	Date of the last administration of trial treatment + 30 days (residual effect period)
Follow-up	Date of the last administration of trial treatment + 31 days	Date of the last per protocol visit

Note: a 30-day residual effect period (REP) is defined for this trial.

For safety analyses, AEs will be classified to one of the following time periods: “Screening”, “On-Treatment” or “Follow-up.” This will be applied for all adverse events. Detailed rule for assigning AEs to these time periods are listed below:

- If the date of informed consent  $\leq$  AE onset date  $<$  date/time of first administration of BI 754091, then the AE is assigned to “Screening”;
- If date/time of first administration of BI 754091  $\leq$  AE onset date  $\leq$  date of last administration of BI 754091 + 30 days, then the AE is assigned to “On-Treatment”;
- If AE onset date  $>$  date of last administration of BI 754091 + 30 days, then the AE is assigned to “Follow-up”

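### The SAP defines treatment-emergent AEs by onset date alone, dropping without declaration the protocol's rule for AEs that begin before dosing and worsen on treatment

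*SAP*

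**What the plan says.** Protocol 7.3.4 gives two routes to treatment-emergent status. The first is by onset: "All AEs with an onset between start of treatment and end of the REP, a period of 30 days after the last dose". The second is by worsening, and it gives the event the same treatment-emergent label: "Adverse events that start before first drug intake and deteriorate under treatment will also be considered as".

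SAP 7.8.1 states one route: "a treatment-emergent AE has an onset in the analysing treatment period". It then fixes the window: "The AE analysis will be based on the on-treatment period which starts with the date of the first administration of study medication". The window closes when the 30-day residual effect period is over. "AEs with an onset date in the screening period", like those in follow-up, go to a separate listing. The frequency tables cover the on-treatment period only.

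SAP 6.1 supplies the assignment rule. Each AE goes to Screening, On-Treatment or Follow-up according to where its onset date falls, and the SAP adds: "This will be applied for all adverse events". No exception is made for an event that worsens after dosing.

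SAP Section 4, which is reserved for departures from the protocol's analysis, contains one item, the CTCAE version: "therefore CTCAE Version 5.0 is not applicable for the primary endpoint in Phase Ia". The definition of treatment-emergent is not mentioned there.

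**The concern.** The two current documents would classify the same event differently, and the SAP is the one a programmer follows. The affected events will be in the database, because Protocol 5.3.6.8.1 collects all AEs "From signing the ICF onwards until the end of treatment", and screening may last up to 28 days.

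What is at stake is the completeness of the on-treatment safety tables in a first-in-human trial. SAP 7.8.1 plans most of them by highest CTCAE grade. An event that was mild at screening and became severe on drug is the kind of case that the protocol's second route is meant to catch. The share of patients with AEs and with SAEs is also a Phase Ib secondary endpoint (Protocol 5.1.2.2, SAP 5.2.2.2). Every event that is treatment-emergent under the SAP is also treatment-emergent under the protocol, but not the reverse, so the difference runs in one direction only, towards lower reported toxicity.

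**Working it through.** The plan has no figure to reproduce. The check applies each document's rule to the same cases and then works out what one patient is worth.

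**Inputs.** Protocol 7.3.4 (two routes, 30-day residual effect period); SAP 6.1 (assignment by onset date); SAP 7.8.1 (definition, window, separate listing); Protocol 3.1 (expansion cohorts of about 30 to 40 patients).

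**Test cases**

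| Case | Protocol 7.3.4 | SAP 6.1 and 7.8.1 |
|---|---|---|
| A. Onset Day -5, Grade 1, no change | Not treatment-emergent | Screening, listed |
| B. Onset Day -5, Grade 1; Grade 3 on Day 20; one record | Treatment-emergent | Screening, listed |
| C. As B, but the worsening is a new record with onset Day 20 | Treatment-emergent | On-Treatment, tabulated |
| D. Onset Day 20 | Treatment-emergent | On-Treatment, tabulated |

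The rules agree on A, C and D and disagree on B. The conflict therefore bites only if a worsening stays on the original record.

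**Do the documents settle which of B or C applies?** Protocol 5.3.6.8.1 asks for worsening of pre-existing conditions to be recorded as an AE or SAE, and treats abnormalities already present before inclusion as baseline conditions. It does not say that an AE opened after consent and before the first dose gets a second record with a new onset date when its grade rises. Protocol 8.3.1 names onset and end dates for AEs but no date of grade change. The SAP is silent on both. So case B is possible under the text as it stands.

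**Weight of one patient**

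- Cohort of 30: 1/30 = 3.3 percentage points on a preferred-term or grade-specific rate.
- Cohort of 40: 1/40 = 2.5 percentage points.

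**Any-AE percentage.** SAP 7.8.1 counts patients, not events. A case-B patient changes this figure only if he or she has no other AE with onset on treatment. Protocol 2.3 cites immune-related AEs in about 70% of patients given anti-PD-1 or anti-PD-L1 antibodies. If that share held here and were unrelated to having a case-B event (both assumptions), at most 30% of case-B patients would have no other on-treatment AE. The expected shift per case-B patient would then be at most 0.30 × 3.3 = 1.0 point in a cohort of 30, or 0.30 × 2.5 = 0.75 point in a cohort of 40. AEs that are not immune-related would reduce it further.

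**The case against.** The strongest defence is that the loss depends on recording practice. The protocol's instruction on worsening of pre-existing conditions is not expressly limited to conditions that predate consent. If sites enter each worsening as a new AE, both rules give the same tables. SAP 7.8.1 also says that the analysis follows the sponsor's standards, which may deal with this but are not reproduced. This stands as far as it goes: omission is possible, not certain. It does not remove the conflict, because the SAP states its own onset-only rule and neither document gives a new-record convention for AEs opened in screening.

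A second defence is that laboratory worsening is captured elsewhere. SAP 7.8.2.1 and 7.8.2.2 tabulate shifts from baseline and, for many parameters, Grade 2 or higher with a rise of at least one grade, whatever the AE onset date. That is a real partial mitigation, but it does not reach clinical events.

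Third, the safety analysis is descriptive with no hypothesis test, so no formal inference is at risk. That is correct, and it limits the severity.

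Some stronger readings are tempting but not supported:

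- A reader might infer that these events vanish from the report. They do not; SAP 7.8.1 lists them separately.
- A reader might infer that the headline AE percentage is materially too low. Patient-level counting makes a large shift unlikely.
- A reader might try to put a number on the affected patients. The documents give no frequency for screening-onset AEs that worsen, so any count would be guesswork.
- A reader might infer that the MTD decision is compromised. The documents do not show this: under Protocol 4.1.5, DLTs in Cycle 1 are identified by Investigator and sponsor review and a dedicated report, not read off the treatment-emergent tables.

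**Conclusion.** The point holds as an undeclared mismatch between two current texts. Followed as written, the SAP would leave a screening-onset AE that worsens on drug out of the on-treatment preferred-term and highest-grade tables, and out of the SAE tables if that event was the patient's only serious one on treatment. This is contrary to Protocol 7.3.4.

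The conclusion rests on one condition: the worsening is kept on the original AE record. The documents leave that open. The direction is certain (understatement only). The total size is unknown. Each affected patient is worth 3.3 points in a cohort of 30 or 2.5 points in a cohort of 40 on the specific rates, and little on the any-AE percentage. The correction is worth making because it is cheap and protects the main safety output, but it does not call the trial's conclusions into question.

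**What to change.** Add the protocol's clause to SAP 6.1 and 7.8.1: an AE with onset before the first dose that deteriorates between the first dose and the last dose + 30 days is assigned to On-Treatment at its worsened grade. That window matches the on-treatment period already used in both documents.

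If the eCRF does not capture the date of grade change, implement the clause by treating a grade increase after the first dose as a new AE record with its own onset date, and state that convention in the SAP. The existing onset-based programs would then give the right result. The trigger should stay with deterioration, as in the protocol; adding a change in seriousness without worsening would be a new rule.

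If the sponsor prefers the narrower definition, SAP Section 4 should declare it as a change from Protocol 7.3.4 and give the reason. That would cure the silence but not the understatement.

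The cost is one SAP rule and a small programming change, or a small data-handling change if worsened events have to be split into separate records.

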## **7.8.2      Laboratory data**

The analysis of laboratory data will be descriptive in nature and will be based on BI standards. The same on-treatment period as considered for the analysis of adverse events will be applied for laboratory values. Patients having at least one post-baseline laboratory value will be displayed in the descriptive analyses. Patients with missing CTCAE grade at baseline or no baseline value but with post-baseline values will be displayed in a new category “missing CTCAE grade at baseline” for those laboratory parameters where CTCAE grading is applicable. CTCAE grades for applicable laboratory parameters will be calculated according to CTCAE Version 5.0.

### **7.8.2.1      Analysis**

The Laboratory tests will be classified into the following categories:

- Primary- full analysis
- Secondary- listing of possible clinically significant values
- Diagnostic- listing of all observed values
- Not analysed

The following outputs will be presented for primary laboratory tests:

- Descriptive statistics, including changes from baseline
- Frequency of patients with shifts from baseline
  - Shifts will be defined in terms of
    - CTCAE grades will be used for laboratory tests with CTCAE grades defined
    - The upper and lower reference limits will be used for laboratory tests without CTCAE grades
- Frequency of patients with possible clinically significant abnormalities (definitions see [Section 7.8.2.2](#))

The analysis of secondary laboratory tests will be limited to tabulation of the frequency of patients with possible clinically significant abnormalities (definitions see [Section 7.8.2.2](#)).

Laboratory tests classified as “diagnostic” are recorded as a follow-up to abnormalities of associated lab tests for diagnostic purposes i.e. amylase and lipase would be measured to investigate possible pancreatitis. These values will be presented in a separate listing. No other analyses will be performed

Analyses of descriptive statistics should use normalized lab values and will be displayed by calculated visit instead of actual visit reported to ensure a common handling of all laboratory assessments and to account for unscheduled visits representing a repeated laboratory measurement (see [Table 6.7: 2](#) and [Table 6.7: 3](#)).

Analyses of frequencies of patients with potential clinical significance, analyses of shift, and liver function categories tables should use converted values.

Baseline for safety laboratory parameters will be the last available measurement before the start of study drug. Laboratory measurements taken up to 30 days after the last administration of study drug will be considered as on-treatment.

Primary laboratory test results will be presented in CTR section 15.

Secondary laboratory test results will be included in Appendix 16.1.13.1.

Diagnostic laboratory test results will be listed in Appendix 16.1.13.1.

Laboratory test that are not analysed will be listed in Appendix 16.2.8.

